1. VERSION HISTORY

This SAP for study PHAROS (C4221008, ARRAY-818-202) is based on the protocol amendment 5 dated 24 Sep 2021.

Table 1. Summary of Changes

Version/ Date	Associated Protocol Amendment	Rationale	Specific Changes
Version 1.0 18 June 2020	Version 2 03 Oct 2019	N/A	N/A
Version 2.0 03 May 2021	Version 4 16 Feb 2021	Following consultation with the FDA, the design of the study has been revised to allow for registration of a treatment naïve population and a previously treated population, either separate or together	
 • Primary endpoint will be confirmed tumor response by independent radiology for treatment naïve participants and previously treated participants with BRAF^{V600E} mutant NSCLC. • Sample size has been calculated for the 2 populations (treatment naïve participants and previously treated participants). • Two interim analyses included. • A sensitivity analysis for ORR by IRR will be performed in RE set. • AESI analyses added. • Substituted the term patient with participant per new Pfizer standard. • Signature page will be an external document.

Table 1. Summary of Changes

Version/ Date	Associated Protocol Amendment	Rationale	Specific Changes
Version 3.0 26 May 2022	Version 5 24 Sep 2021	Following consultation with the FDA after first interim analysis, the second interim analysis was removed and PCD was defined	
 • Removed the second interim analysis. • Specified the timing of final ORR analysis (PCD) for treatment-naïve participants. • Specified the RE set will be used at the time of interim analysis. Aligned TTR (secondary endpoint) to protocol amendment 5. • Modified the description of some AE tables. • Added evaluation of differences between treatment-naïve and previously treated participants for log-transformed PK parameter estimates (AUC_{0-6}, AUC_{τ}, and C_{\max}) for analytes (encorafenib, LHY746, and binimetinib) by visit day (C1D1 and C1D15).

2. INTRODUCTION

This document describes the statistical analyses and data presentations to be performed for the clinical protocol ARRAY-818-202 entitled “A Phase 2, Open-label Study of Encorafenib + Binimetinib in Patients with $BRAF^{V600}$ -Mutant Non-small Cell Lung Cancer (NSCLC).”

This SAP should be read in conjunction with the study protocol and eCRFs. This document has been developed using the protocol Version 5 dated 24 September 2021 and eCRFs dated 18 October 2021. Any further changes to the protocol or eCRFs may necessitate updates to the SAP.

This SAP provides a comprehensive and detailed description of the strategy, rationale, and statistical techniques to be used to assess the efficacy, safety, PK, and biomarker analyses of encorafenib + binimetinib in participants with $BRAF^{V600}$ -Mutant NSCLC as outlined in the protocol.

Statistical analyses detailed in this SAP will be conducted using SAS[®], Version 9.4 or higher (SAS Institute, Inc., Cary, NC USA). Noncompartmental PK analyses will be performed with Phoenix[®] WinNonlin[®] Version 8.0 or higher (Certara USA, Inc., Princeton, NJ). Data displays will adhere generally, if not specifically, to the standard mock tables, listings, and figures and can be found in a separate SAP shell document.

2.1. Responsibilities

A Sponsor or CRO-designated Biostatistician or Statistical Programmer will perform any statistical analyses required for participant disposition, protocol deviations, participant characteristics, efficacy, and safety and is responsible for the production and quality control of all tables, figures, and listings associated with these analyses. A Sponsor or CRO-designated Clinical Pharmacology representative will perform any PK statistical analyses and is responsible for the production and quality control of all tables, figures, and listings associated with these analyses. A Sponsor Translational Science representative will perform any biomarker statistical analyses and is responsible for the production and quality control of all tables, figures, and listings associated with these analyses.

3. STUDY OBJECTIVES, ENDPOINTS AND ESTIMANDS

3.1. Study Objective and Endpoints

Table 2. Objectives and Endpoints

Primary Objective	Primary Endpoint

 To evaluate the efficacy of encorafenib + binimetinib in treatment-naïve and previously treated participants with BRAF^{V600E}-mutant NSCLC as measured by ORR 	
 ORR defined as the proportion of participants who have achieved a confirmed best overall response (CR or PR) as determined by IRR per RECIST v1.1 in the treatment-naïve setting ORR defined as the proportion of participants who have achieved a confirmed best overall response (CR or PR) as determined by IRR per RECIST v1.1 in the previously treated setting
Secondary Objectives	Secondary Endpoints

 To evaluate the efficacy of encorafenib + binimetinib in treatment-naïve and previously treated participants with BRAF^{V600E}-mutant NSCLC as measured by DOR, DCR, PFS, and TTR 	
 Confirmed ORR by investigator per RECIST v1.1 DOR (by IRR and investigator) defined as the time from the date of the first documented response (CR or PR) that is subsequently confirmed to the earliest date of disease progression, per RECIST v1.1, or death due to any cause DCR (by IRR and by investigator) defined as the proportion of participants who have achieved a confirmed CR, confirmed PR or SD per RECIST v1.1

Table 2. Objectives and Endpoints

	
 • PFS (by IRR and by investigator) defined as the time from the date of first dose of study drug to the earliest date of disease progression, per RECIST v1.1, or death due to any cause • TTR (by IRR and by investigator), defined as the time from the date of first dose to the first documentation of objective response (CR or PR) which is subsequently confirmed (by IRR and by Investigator)

 • To evaluate the efficacy of encorafenib + binimetinib in treatment-naïve and previously treated participants with BRAF^{V600E}-mutant NSCLC with respect to OS 	
 • OS defined as the time from the date of first dose of study drug to the date of death due to any cause

 • To evaluate the safety and tolerability of encorafenib + binimetinib in treatment-naïve and previously treated participants with BRAF^{V600E}-mutant NSCLC 	
 • Incidence and severity of AEs graded according to the NCI CTCAE v4.03 and changes in clinical laboratory parameters, vital signs, ECGs and ECHO/MUGA scans
Exploratory Objectives	Exploratory Endpoints

 • To evaluate the PK of encorafenib, its metabolite LHY746, and binimetinib in participants with BRAF^{V600E}-mutant NSCLC 	
 • Plasma concentration-time profiles and PK parameter estimates for encorafenib, its metabolite LHY746, and binimetinib

 • To assess blood ctDNA mutation status 	
 • Genomic analysis of ctDNA in blood samples

3.2. Primary Estimand

The primary estimand of the study will be Objective Response defined as follows:

- Analysis Population: all participants with *BRAF*^{V600E}-mutant (based on local test) NSCLC who receive at least 1 dose of study drug.
- Variable: Objective response defined as CR or PR according to RECIST v1.1 based on IRR assessment, from the date of first dose of study treatment until the date of the first documentation of PD, death or start of new anticancer therapy. Both CR and PR must be confirmed by repeat assessments performed no less than 4 weeks after the criteria for response are first met.
- Population-level summary measure: proportion of participants who have achieved a confirmed BOR of CR or PR as determined by IRR per RECIST v1.1 and corresponding exact two-sided 95% CI.

4. INVESTIGATIONAL PLAN

4.1. Overall Study Design and Plan

This is an open-label, multicenter, non-randomized, Phase 2 study to determine the safety, tolerability, and efficacy of encorafenib given in combination with binimetinib in treatment-naïve and previously treated participants with *BRAF*^{V600}-mutant metastatic NSCLC. Participants who are either treatment-naïve, or who have received 1) first-line treatment with standard platinum-based chemotherapy, or 2) first-line treatment with an anti-PD-1/PD-L1 inhibitor given alone or in combination with platinum-based chemotherapy will be enrolled. Treatment will be administered in 28-day (\pm 3 days) cycles and will continue until disease progression, unacceptable toxicity, withdrawal of consent, start of subsequent anticancer therapy, or death. Once the participant discontinues study treatment, the treatment period will end, and the participant will enter the follow-up period for safety, subsequent anticancer therapy, disease status, and survival status; participants who discontinue treatment for reasons other than PD will continue to have radiographic assessments every 8 or 12 weeks until PD or subsequent anticancer therapy.

Additional information regarding eligibility criteria, planned dose levels, schedules of assessments, and other study design details and procedures are detailed in the clinical study protocol.

4.2. Statistical Hypotheses

The primary endpoint of the study is ORR for treatment-naïve and previously treated participants as determined by IRR per RECIST v1.1.

The study is designed to test the null hypothesis of $ORR \leq 39\%$ for treatment-naïve participants with *BRAF*^{V600E} NSCLC, which is considered not sufficiently clinically meaningful to warrant further study on encorafenib and binimetinib in this indication where similar therapies are already available. The alternative hypothesis is $ORR > 39\%$ with the assumption that the true ORR is $\geq 65\%$. Hypotheses are based on the results observed in the dabrafenib plus trametinib study in *BRAF*^{V600E}-mutant NSCLC participants, in which the ORR per investigator assessment was 64% (95% CI: 46, 79) for treatment-naïve participants (Planchard et al 2017⁵), and the results observed in participants with NSCLC whose tumors expressed PD-L1 levels with a TPS $\geq 50\%$ and received pembrolizumab as a single agent (Keynote-042) in which ORR per IRR was 39% (95% CI: 34, 45) (Mok et al 2019⁴).

For previously treated participants with *BRAF*^{V600E} NSCLC, the null hypothesis of $ORR \leq 20\%$ will be tested. The alternative hypothesis is $ORR > 20\%$ with the assumption that the true ORR is $\geq 45\%$. This hypothesis is based on the ORR of 18% (95% CI: 14, 23) observed in previously treated participants with NSCLC whose tumors expressed PD-L1 levels with a TPS $\geq 1\%$ and who received pembrolizumab as a single agent (Keynote-010; Herbst et al 2016²).

4.3. Sample Size Considerations

The sample size calculation is based on the primary endpoint of ORR as determined by IRR per RECIST v1.1. The hypotheses to be tested are described in [Section 4.2](#).

At least 60 treatment-naïve and 37 previously treated $BRAF^{V600E}$ NSCLC participants will be enrolled and treated. It is not expected that more than 107 participants with any $BRAF^{V600}$ mutation will be enrolled and treated.

With 60 evaluable treatment-naïve participants with $BRAF^{V600E}$ NSCLC, the power is greater than 95% to test the null hypothesis that the ORR $\leq 39\%$ versus the alternative hypothesis that it is $> 39\%$ assuming an alternative target rate of 65% with a one-sided $\alpha \leq 0.025$ based on a single-stage design using exact test. The null hypothesis will be rejected if ≥ 32 confirmed objective responses are observed out of 60 participants.

With 37 evaluable previously treated participants with $BRAF^{V600E}$ NSCLC, there is at least 90% power to test the null hypothesis that the ORR $\leq 20\%$ versus the alternative hypothesis that it is $> 20\%$ assuming an alternative target rate of 45% with a one-sided $\alpha \leq 0.025$ based on a single stage design using exact test. The null hypothesis will be rejected if ≥ 13 confirmed objective responses are observed out of 37 participants.

5. ANALYSIS SETS

5.1. Screened

Screened participants include all participants who sign the ICF.

5.2. Safety Analysis Set

The SS includes all participants who receive at least 1 dose of study treatment.

Unless otherwise specified, the safety analysis set will be the default analysis set used for all efficacy and safety analyses.

5.3. Response Evaluable Set

The RE set will be used for a sensitivity analysis of ORR by IRR at the time of the interim analysis. RE is defined as all participants in the SS who have an adequate baseline disease assessment and meet at least 1 of the following 2 criteria:

- Had at least one post-baseline disease assessment at least 6 weeks from first dose;
- Withdrew from the study or experienced progressive disease/death at any time on study.

5.4. PK Analysis Set

The PK analysis set includes all participants in the SS who have at least 1 postdose PK blood collection after the first dose of study treatment with associated bioanalytical results. The PK analysis set will be used for summaries of PK data.

6. CHANGES FROM THE STUDY PROTOCOL

This SAP incorporates the following changes from the statistical analyses described in the study protocol:

- Removed the second interim analysis and defined the time of final ORR analysis (Primary Completion Date) for treatment-naïve participants;
- Included RE set for a sensitivity analysis of ORR by IRR to be conducted at the time of the interim analysis;
- Substituted the term patient with participant per new Pfizer standard;
- [Section 8.4.3](#) Safety Analysis: clinically notable measurements will not be summarized for laboratory data. No descriptive summary will be created for ECOG performance status.

7. STATISTICAL METHODS

7.1. Reporting Conventions and Definitions

All tables will include 3 columns/groups: “Treatment Naïve”, “Previously Treated”, “Total”.

7.1.1. Baseline

Baseline is defined as the last available and valid assessment before or on the start date of study treatment. If an assessment is planned to be performed prior to the first dose of study treatment in the protocol and the assessment is performed on the same day as the first administration of study treatment and the time is unknown, it will be assumed that it was performed prior to study treatment administration unless the protocol specifies it otherwise. Unscheduled assessments will be used in the determination of baseline. Data reported at the End of Treatment (EOT) visit are not eligible for baseline selection. The ECG baseline will be the average of triplicate ECG measurements obtained before the start of treatment on Day 1 of Cycle 1 (C1D1), or on screening, if baseline assessment is missing.

7.1.2. Last Contact Date

Last contact date will be derived for participants not known to have died on or before the analysis cutoff date. Imputed dates will not be considered for the determination of last contact date. Only dates associated with participant visits or the actual assessment of the participant will be used in the derivation. Dates associated with a technical operation unrelated to participant status (e.g., the date a blood sample was processed) will not be used. Last contact date will only be derived using the latest complete date among the following:

- Study drug start and end dates with non-missing dose (doses of 0 are allowed)
- RECIST assessment date with evaluation marked as done
- Laboratory/PK collection date with sample collection marked as done

- Vital sign, ECG, physical exam, dermatologic exam, and ophthalmic exam assessment dates with non-missing parameter value
- ECOG performance status date with non-missing performance status
- Start/end date of AEs with non-missing verbatim term
- Start/end date of anticancer therapies administered after study treatment; discontinuation with non-missing medication/procedure term
- Start/end date of concomitant medications/non-drug treatments/procedures
- Date of contact for most recent post-treatment survival assessment with the status as “Alive”
- Cardiac imaging assessment date
- Biomarker collection date.

7.1.3. Study Day

Study day is defined in the following manner:

- On or after the start date of study treatment: (date of assessment/event) – (treatment start date) + 1. Day 1 will therefore be the first day of study treatment.
- Before the start date of study treatment: (date of assessment/event) – (treatment start date).

7.1.4. On-treatment Period

On-treatment period is defined as the time from the first dose date of study treatment to the last dose of study drug administration date (when both drugs are permanently discontinued) + 30 days or the earliest date of subsequent anti-cancer drug therapy minus 1 day, whichever occurs first.

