7.1.4. Post-treatment Follow-up

Cutaneous squamous cell carcinoma has been observed in patients treated with BRAF inhibitors including encorafenib. It is recommended that dermatologic screening for skin malignancies be performed every 8 weeks until 6 months after the last dose of encorafenib. Patients should be instructed to immediately inform the Investigator if new skin lesions develop.

7.1.4.1. 30-Day Safety Follow-up

The safety follow-up period is the interval between the EOT visit and the scheduled followup visit, which should occur 30 days (+ 7 days) after the EOT visit (or after the last dose of study treatment if the EOT was not performed). Adverse events and SAEs must be reported as outlined in Section 7.5.1.1 and Section 7.5.1.2. Information related to AEs (including concomitant medication taken for ongoing AEs) and new anticancer therapies will be collected. Reasonable efforts should be made to have the patient return for the safety followup visit and report any AEs that may occur during this period. If the patient is scheduled to start a new anticancer therapy before the end of the 30-day follow-up period, the safety follow-up visit should be performed before the new anticancer therapy is started.

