7.3.4. Dermatological Examinations

Dermatologic evaluations will be performed at the site by the Investigator to monitor for the possible development of keratoacanthoma and/or squamous cell carcinoma, as these have been reported to occur with selective BRAF inhibitor treatment (Flaherty et al, 2010; Kefford et al, 2010; Robert et al, 2011). This assessment may be performed predose or postdose at the time points specified in the SoA (Table 3).

In addition, dermatologic screening for skin malignancies will be performed every 8 weeks until 6 months after the last dose of encorafenib (see Section 7.1.4).

In case of occurrence of keratoacanthoma or squamous cell carcinoma, patients will undergo complete surgical excision of the skin lesion following institutional standards. Dermatologic evaluations will be performed by a dermatologist as clinically indicated.

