7.5.1. Time Period and Frequency for Collecting AE and SAE Information

As of IRB/IEC approval of Amendment 3, the time period for actively eliciting and collecting AEs and SAEs ("active collection period") for each patient begins from the time the patient provides informed consent, which is obtained before the patient's participation in the study (ie, before undergoing any study-related procedure and/or receiving study treatment), through and including a minimum of 30 calendar days, except as indicated below, after the last administration of the study treatment. *Note*: Prior to IRB/IEC approval of Amendment 3 only study procedure related AEs were required to be reported from the time the patient provided informed consent up to the first dose of study treatment.

During the long-term follow up period in this study for survival, only SAEs will be actively elicited and collected after completion of the active collection period described above. The SAEs identified during long-term follow-up will be reported to Pfizer Safety on the CT SAE Report Form only if considered reasonably related to the study treatment.

Follow-up by the investigator continues throughout and after the active collection period and until the AE or SAE or its sequelae resolve or stabilize at a level acceptable to the investigator and Pfizer concurs with that assessment.

For patients who are screen failures, the active collection period ends when screen failure status is determined.

If the patient withdraws from the study and also withdraws consent for the collection of future information, the active collection period ends when consent is withdrawn.

If a patient definitively discontinues or temporarily discontinues study treatment because of an AE or SAE, the AE or SAE must be recorded on the CRF and the SAE reported using the CT SAE Report Form.

Investigators are not obligated to actively seek AEs or SAEs after the patient has concluded study participation. However, if the investigator learns of any SAE, including a death, at any time after a patient has completed the study, and he/she considers the event to be reasonably related to the study treatment, the investigator must promptly report the SAE to Pfizer using the CT SAE Report Form.

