7.5.1.2. Recording Nonserious AEs and SAEs on the CRF

All nonserious AEs and SAEs occurring in a patient during the active collection period, which begins after obtaining informed consent as described in Section 7.5.1, will be recorded on the AE section of the CRF.

The investigator is to record on the CRF all directly observed and all spontaneously reported AEs and SAEs reported by the patient.

If a patient begins a new anticancer therapy, the recording period for nonserious AEs ends at the time the new treatment is started; however, SAEs must continue to be recorded on the CRF during the above-indicated active collection period. Note that a switch to a commercially available version of the study treatment is considered as a new anticancer therapy for the purposes of SAE reporting.

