7.6.4. Adverse Events

Treatment-emergent adverse events (TEAEs) are defined as AEs with onset date during the on-treatment period.

Unless otherwise stated, only TEAEs will be presented in summary tables. However, all AEs will be presented in listings. AEs and SAEs will be coded by PT and SOC using the latest available MedDRA version.

The severity of an AE will be assessed by the investigator using the NCI CTCAE, Version 4.03. For participants with more than 1 AE within a SOC or PT, only the highest grade will be included in by-severity summaries.

The investigator will also assess whether the AE is related to study drugs (i.e., a treatment-related AE). For participants with more than 1 AE within a SOC or PT, the highest level of relationship (related is higher than not related) will be included in the by relationship summaries. AEs will be considered treatment related if they are related to encorafenib and/or binimetinib.

For summaries by SOC and PT, each participant will be counted at most once per SOC and at most once per PT. For summaries by PT, each participant will be counted at most once per PT.

Overall summary of safety table will include numbers and percentages of the following:

- Participants with at least 1 TEAE regardless of causality
- Participants with at least 1 treatment-related TEAE
- Participants with Grade 3 or 4 TEAEs
- Participants with Grade 3 or 4 treatment-related TEAEs
- Participants with Grade 5 TEAEs
- Participants with Grade 5 treatment-related TEAEs
- Participants with at least 1 treatment-emergent SAE
- Participants with at least 1 treatment-related SAE
- Participants who discontinued study drug due to a TEAE regardless of causality
 - TEAE leading to encorafenib discontinuation
 - TEAE leading to binimetinib discontinuation
- Participants with a dose reduction due to a TEAE
 - TEAE requiring encorafenib dose reduction
 - TEAE requiring binimetinib dose reduction
- Participants with a dosing interruption due to a TEAE
 - TEAE requiring encorafenib dosing interruption
 - TEAE requiring binimetinib dosing interruption

All TEAE summaries will be displayed (frequency counts and percentages) alphabetically by system organ class (SOC) and preferred term (PT) by descending frequency within SOC

based on “Total” group, if not otherwise noted. Individual summary tables showing the incidence of participants with the following subsets of TEAEs will be generated:

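### Skin screening runs to 6 months after the last encorafenib dose, but malignancies starting after day 30 enter no AESI table, and late non-serious lesions have no required AE record

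*SAP*

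**What the plan says.** **Screening.** Protocol 7.3.4 states that "dermatologic screening for skin malignancies will be performed every 8 weeks until 6 months after the last dose of encorafenib". Protocol 7.1.4 gives the same interval but only recommends it. The dermatologic row of Table 3 has exams every 8 weeks on treatment, at EOT and at the safety follow-up visit, and its note marks post-treatment follow-up as required, with a pointer to 7.3.4. The stated reason is cutaneous squamous cell carcinoma and keratoacanthoma under BRAF inhibition. Protocol 2.1.4 puts new primary malignancies first among the important potential adverse effects, and 7.5.8 takes the AESIs from that section.

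**Collection.** Protocol 7.5.1 collects all AEs "through and including a minimum of 30 calendar days, except as indicated below, after the last administration of the study treatment". In long-term follow-up, "only SAEs will be actively elicited and collected after completion of the active collection period described above". If a new anticancer therapy begins, "the recording period for nonserious AEs ends at the time the new treatment is started" (7.5.1.2), while SAE recording continues within the active period. Protocol 7.1.4.3 asks sites, after the 30-day period, to record new SAEs considered related.

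**Analysis.** SAP 7.1.4 defines the on-treatment period as first dose "to the last dose of study drug administration date (when both drugs are permanently discontinued) + 30 days", or to the day before subsequent anticancer drug therapy if that is earlier. SAP 7.6.4 defines a TEAE by onset within that period and adds: "Unless otherwise stated, only TEAEs will be presented in summary tables". All AEs go into listings.

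**The concern.** The surveillance window was set for one delayed class effect. The table window is the generic 30-day rule, and nothing links the two. Patients are examined for about five months beyond the point at which a finding can contribute to a reported incidence or time to onset. For lesions judged non-serious, there may be no AE record to report.

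Safety and tolerability is a secondary objective, and Version 4 of the protocol was written to support registration. At stake is whether a reader of the safety tables can see how often these lesions occurred over the period in which the sponsor chose to look for them.

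**Working it through.** The plan gives no figure on this point to reproduce. The check compares windows and follows each type of late lesion through the rules.

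**1. Anchor.** Screening runs from the last encorafenib dose. The SAP period runs from the last dose once both drugs have stopped. Protocol 6.6.1 requires binimetinib to stop when encorafenib is permanently stopped, so the two anchors are about the same day.

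**2. Window lengths.** SAP 7.1.9 sets 1 month = 30.4375 days.
- Screening window: 6 × 30.4375 = 182.6 days.
- Table window: at most 30 days.
- Screened but not tabulated: 182.6 − 30 = 152.6 days, and 152.6 / 182.6 = 84%. The share is larger if new drug therapy starts before day 30.

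**3. Exam dates.** If the 8-week clock restarts at the last dose, exams fall on days 56, 112 and 168, all after day 30. If it carries on from the on-treatment schedule, 2 or 3 of the 3 or 4 exams fall after day 30. The SAP rule uses onset date, so exam dates are only a proxy: a lesion found on day 56 but dated to before day 30 would still count as treatment-emergent unless new drug therapy had already started.

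**4. A skin malignancy with onset after day 30:**
- *Serious, judged related:* elicited (7.5.1), recorded (7.1.4.3) and listed (SAP 7.6.4). It enters no table.
- *Serious, judged unrelated:* 7.5.1 says SAEs are collected, but 7.1.4.3 asks only for related ones to be recorded. The two do not clearly agree.
- *Non-serious:* outside the active collection period, so no AE record is required.

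**5. Other routes.**
- The AESI tables in SAP 7.6.4 are either labelled treatment-emergent or fall under the default rule. None states an exception.
- SAP 7.6 has no section for dermatologic findings. Exam dates are used only to derive last contact (SAP 7.1.2).
- Protocol 7.5.8 sends AESIs back to the collection rules of 7.5.1 to 7.5.1.2.
- Deaths are the one safety outcome that SAP 7.6.4 summarises beyond 30 days.

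**6. Number of events.** Protocol 2.1.4 gives 2.6% for squamous carcinoma/keratoacanthoma, with a median of 5.8 months to first occurrence, from the melanoma study. Applied to 97 (60 + 37) or 107 patients, this gives 0.026 × 97 = 2.5 or 0.026 × 107 = 2.8 cases over the whole observation period. The share with onset after day 30 is not given. Purely as an assumption, take a late incidence of 0.5% to 2.6% in 107 patients:
- Expected events: 107 × 0.005 = 0.5 to 107 × 0.026 = 2.8.
- Chance of at least one: 1 − 0.995^107 = 42% to 1 − 0.974^107 = 94%.

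That range is too wide to say whether any event would be missed.

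**The case against.** The case on the other side has several sound parts.

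- **SAE collection does not end at day 30 or at new therapy.** Appendix 4 (14.2) names invasive or malignant cancers among events that should usually be considered serious, and 14.3 treats an event of unknown causality as related for reporting. Most late squamous cell carcinomas should therefore reach the CRF and the listings.
- **Table 3 schedules exams at EOT and at the safety visit**, and these can feed the 30-day tables. This stands with one qualification: 7.1.4.1 times the safety visit from the EOT visit. If EOT is even one day after the last dose, a visit on its nominal date falls past last dose + 30 days.
- **Typical onset may be on treatment.** Median first occurrence is 5.8 months, while Protocol 2.1.2 gives a median PFS of 10.2 to 10.9 months for the comparator BRAF/MEK combination in NSCLC. If treatment here lasts about as long (an assumption), most cases will be tabulated.
- **The TEAE window is openly defined.** Ending it at new drug therapy avoids charging this regimen with events under another drug.

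These points limit the size of the gap and are good reasons to leave the 30-day tables alone. They do not supply a table for later onset, or a recording rule for late lesions judged non-serious.

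**Conclusion.** The gap is real but narrow. Any skin malignancy with onset after last dose + 30 days, or after new anticancer drug therapy starts, is absent from every AESI incidence and time-to-onset table. Late lesions judged non-serious need not be recorded as AEs, and the rule for late unrelated SAEs is unclear. The uncovered time is about 84% of the post-dose screening window. The number of events in it is unknown. ORR and the other efficacy analyses are untouched.

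A reader might infer that AE collection stops at 30 days and that these cancers vanish from the safety result. The documents do not support that: related SAEs continue to be collected and are listed, and events on treatment or within 30 days are tabulated unless new drug therapy came first. A reader might also infer that one or two cases would be missed and the rate understated by a third. No post-treatment share is given, so that cannot be claimed. The existing tables report treatment-emergent incidence as defined and are not wrong on their own terms.

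The conclusion assumes that the separately held AESI list follows Protocol 2.1.4 and includes new primary malignancies. The change is a low-cost improvement to completeness, not the correction of an error in the main safety tables.

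**What to change.** 1. **SAP 7.6.4:** leave the 30-day tables unchanged. Add one supplementary summary of new primary malignancies, with time to onset, from first dose to last encorafenib dose + 6 months. Flag events that start after new anticancer therapy.
2. **Protocol 7.5.1:** state that new skin malignancies found within the existing screening window are recorded regardless of seriousness or new therapy. The clause there already allows for exceptions. Align 7.5.1 and 7.1.4.3 on late SAEs judged unrelated.
3. **Protocol 7.1.4, 7.3.4 and Table 3:** reconcile whether the post-treatment screening is recommended or required.

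**Cost.** No new visits, since the exams are already specified. The collection wording needs a short protocol amendment with IRB/IEC approval and an eCRF wording change; the SAP needs one extra table. SAP version 3.0 already follows the first interim analysis, so late data may be incomplete for patients who are already off treatment. Some late events will be confounded by later therapy, which the flag makes visible but does not resolve.
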